The intervention study and follow up is performed as a pragmatic study and includes, with a few exceptions, all newly injured patients with SCI admitted to primary highly specialized rehabilitation at CSCI. Patients will be included during a time period of 18 months corresponding to approximately 50 – 60 patients. Due to the rareness of the morbidity a power calculation is not performed for the primary outcome prior to the intervention, but it is assumed that the total participant number in the intervention and in the historic control cohort, will be comparable to the existing scientific literature.

Numeric continuous data collected at admission, discharge and follow up is reported descriptively as mean and standard deviation together with 95% confidence intervals, or as median, upper and lower quartile as well as interquartile range. Changes over time is reported on the basis of paired ttest. In subproject 3 and 4 the reliability of the outcome measures is analyzed by paired t-test, Pearson's product moment correlation and coefficient of variation or Intraclass correlation coefficient between the test- retest sessions.

Recruitment of participants:

All newly injured patients who are admitted for rehabilitation at CSCI during the project period are included in the primary intervention study as it becomes a part of usual care during the project period. The patients are identified by the primary investigator through internal lists of all inpatients and future admissions. Information about the study is provided to the patients by the Ph.D student and informed consent is retrieved in order to use anonymized data relevant to the study. Likewise

all newly injured patients who are admitted for rehabilitation at CSCI or SCI Center of Western Denmark during the prospective representative national survey (substudy 1) are included and information about the study is provided to the patients and informed consent is retrieved. The patients are informed by the Ph.D student within two weeks after admission to CSCI. The information (in writing and oral) takes place at the patients bed with the door closed and when no other actions in relation to the patient are taking place. The patient is informed that he/she may discuss participation with close relatives before deciding participation, and that he/she may await deciding participation until relatives (or other another person) are able to discuss participation in the study with the Ph.D student together with the patient. Informed consent is ideally retrieved within 2 weeks after admission, and the patients will have at minimum 24 hours to decide whether to participate, but the patient will be given all the time needed to decide whether to participate or not.

Ethical considerations

During the intervention period all newly injured patients who are admitted for rehabilitation are offered the treatment and tests included in the intervention to the extent they are able to participate depending on eg. the level of lesion and completeness of the injury, as this is a part of usual care and will continue as a part of usual care after termination of the project. The intervention in the project is closely related with the content of the present rehabilitation, why the risk of pain and discomfort related to the elements in the intervention is considered modest. There are no side effects to the intervention.

It is assumed that any risks is by far surpassed by the therapeutic gains such as an expected risk reduction of cardiovascular disease and consequently mortality.

Any unintended events related to the elements of the intervention is reported according to existing guidelines. Any compensation is covered by the normal procedures for patients entitled to compensation for unintended harm during their hospitalization.

Funding and organization

This work was initiated and supported by a mutual cooperation about the research program "Centre for Integrated Rehabilitation of Cancer Patients (CIRE) - Neuro/Psychology", between the University Hospitals Centre for Health Care Research (UCSF), University hospital Copenhagen,

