A user panel consisting of both newly injured as well as experienced people with SCI was established and involved in the early phase of the protocol development. All the participants were

¹ The completeness of the injury is graded according to the ASIA Impairment Scale (AIS). AIS is used to determine the degree of motor and sensory function below the level of the SCI. A complete or incomplete injury is defined as absence or presence of sensory and motor function in the most caudal sacral segment. A = complete; B = sensory incomplete without motor function > 3 levels below the motor level of injury on both sides of the body; C = motor incomplete, with preserved motor function below the level of injury and where > 50% of the key muscles below the injury level have a degree < 3 by MMT; D = motor incomplete with preserved motor function below the level of injury and where > 50% of key muscles below the injury level have a degree > 3 by MMT; E = normal sensory and motor function in all segments.

hospitalized at CSCI when they were interviewed about their perception of the present health promoting practice at the clinic. The user panel called for more information in the early phase of rehabilitation about cardiovascular risk, PA and diet as well as more support and guidance about being physical active and appropriate diet, which is the main aim of the project.

Primary study. A systematic interdisciplinary multimodal intervention which, as a part of usual care, facilitates PA, healthy diet and maintenance after discharge through strategic patient education, with the aim of decreasing cardiovascular risk

This pre-post study includes all patients with a new SCI who are admitted at CSCI during a period of 12- 18 months including follow up 6 months after discharge from primary rehabilitation.

Approximately 70 patients with a new SCI are admitted to CSCI annually and with a great variation in length of rehabilitation. Therefore complete data sets from admission to follow up are expected for approximately 50-60 patients during this period.

Intervention

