Patient education is generally carried out by all the health care professions in different educational settings of patients and their relatives [25, 26], with a focus on clarifying the importance of PA and a healthy diet. The overall strategic approaches to cardiovascular risk factors, beginning at the onset of the primary SCI rehabilitation and integrated into the existing setting at predetermined time points throughout the rehabilitation continuum, constitutes the aims for secondary and tertiary cardiovascular prevention. This involves training sessions [27], and feedback on physiological outcome measures and tests, that also serves as motivational tools. Additionally, a motivational conversation, goal setting meetings, tools for shared decision making [28] [24] [29], and use of mentors with SCI are also integrated as components supporting decision making about PA and healthy diet habilitation.

All components of the strategic intervention are offered the patients as a mandatory part of the systematic intervention, ensuring that information and education of the patients is provided and decisions about PA and healthy diet are made. However, the extent to which the patients engage in ie. decision making and goalsetting about PA and healthy diet) is an individual decision. Deciding not to set goals or make decisions about PA and healthy diet, is respected by the interdisciplinary health care professionals in respect of the patients autonomy.

Several outcome measures used to evaluate the intervention at admission, discharge and at follow up 6 months after discharge, are also part of the intervention as a motivational component.

In contrast to the original statistical analysis plan, not all outcomes were analyzed as intended. Therefore, in the present revised statistical analysis plan, outcomes not analyzed as intended are listed as tertiary outcomes with the intention of being analyzed in a subsequent analysis.

comprises of the following:

Primary outcome: Physical capacity (VO2peak)

Secondary outcomes: Body Mass Index (BMI), body composition, Dual- energy X-ray

Absorptiometry (DEXA),, neurological status (International

Standards for Neurological Classification of Spinal Cord Injury (ISNCSCI)),

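### The paired t-test measures VO2peak change only in patients tested at both visits, and testing depends on injury severity, so the change may be biased for the full cohort

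*Combined protocol and SAP*

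**What the plan says.** The Statistics section covers change in a single sentence: "Changes over time is reported on the basis of paired ttest". The Outcome measures section plans three visits: admission, discharge and six months after discharge. VO2peak is the primary outcome. In the text available I find no statement of which pair of visits is primary, no rule for missing VO2peak values or for patients who cannot do the test, and no sensitivity analysis.

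Eligibility is broad: consenting adults with a recent injury enter whatever its cause, level or completeness. Ethical considerations says that treatment and tests are offered as far as the patient can take part, and names lesion level and completeness as determinants.

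The patient numbers appear twice. The primary-study section says "Approximately 70 patients with a new SCI are admitted to CSCI annually and with a great variation in length of rehabilitation", recruits "during a period of 12- 18 months including follow up 6 months after discharge from primary rehabilitation", and concludes that "complete data sets from admission to follow up are expected for approximately 50-60 patients during this period". The Statistics section says "Patients will be included during a time period of 18 months corresponding to approximately 50 – 60 patients". The same 50–60 is thus a count of complete data sets in one place and of patients included in the other.

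**The concern.** A paired t-test drops every patient who lacks one of the two values. If the dropped patients would have changed by a different amount from those kept, the mean paired change does not describe the cohort the study sets out to describe.

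Here the missing tests are unlikely to be a random subset. The plan itself links testing to injury level and completeness. Sub study 2 adds that poor condition can prevent a patient from reaching VO2peak. Complete injuries also stay longer on average (110 and 123 days, against 85 and 86 for incomplete injuries). In a fixed period that must contain the six-month follow-up, longer stayers are therefore less likely to reach the last visit.

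The admission-to-discharge gain and the result on maintenance after discharge are both at stake. Loss before follow-up affects only comparisons that use the follow-up visit; such a patient still contributes to the admission–discharge pair.

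**Working it through.** **1. The plan's own figure.** Inputs: 70 admissions a year and a period of 18 months including six months of follow-up (primary-study section), and the mean lengths of stay given later in that section. With no dropout and no untestable patients,

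patients reaching follow-up = (70/12) × (18 − 6 − stay in months), with 30.44 days to a month.

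| Mean stay (days) | Months open for inclusion | Patients |
|---|---|---|
| 85 | 9.21 | 53.7 |
| 86 | 9.17 | 53.5 |
| 110 | 8.39 | 48.9 |
| 123 | 7.96 | 46.4 |

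The calendar alone gives about 46–54, close to the lower end of 50–60. A 12-month period would give only 11–19. The forecast therefore makes no visible allowance for missed tests, and it is not evidence of how many there will be.

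**2. What complete pairs estimate.** Let p be the share of patients without a pair. Then

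bias = p × (mean change with a pair − mean change without a pair).

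The bias is zero if the two groups change alike, and otherwise can have either sign.

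**3. Illustrative size.** The introduction cites a 24% rise in VO2peak in early rehabilitation. Take 24% as the change in complete pairs, and let r be the change in unpaired patients relative to paired ones. The whole-cohort change is 24 × [(1 − p) + p × r]. Both p and r are assumptions.

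| p | r = 0 | r = 0.5 | r = 1 | r = 1.5 |
|---|---|---|---|---|
| 10% | 21.6% | 22.8% | 24.0% | 25.2% |
| 20% | 19.2% | 21.6% | 24.0% | 26.4% |
| 28.6% | 17.1% | 20.6% | 24.0% | 27.4% |

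Over this range the paired result runs from 6.9 percentage points too high to 3.4 too low.

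**4. Would a mixed model do better?** Simulation with assumed values: 70 patients, true changes +0.15 (admission to discharge) and +0.05 (discharge to follow-up), SD 0.35, correlation 0.75 between visits, 18% of admission and 30% of follow-up tests missing, more often in the less fit (log-odds slope 1.5 per SD). The mixed model has a random intercept and no injury covariates.

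| Missingness follows | Paired | Mixed model |
|---|---|---|
| the observed discharge value | +0.166 / +0.022 | +0.148 / +0.050 |
| fitness at the missed visit itself | +0.135 / +0.078 | +0.123 / +0.096 |
| a stable, unobserved fitness level | +0.147 / +0.051 | +0.133 / +0.070 |

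The standard error is about 0.035 for either method. With purely random missingness both are unbiased. The mixed model wins in the first row and loses in the other two.

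**5. Loss that depends on the unseen change.** In a second assumed setting (60 patients, baseline 15, SD 5, true change 3.6, residual SD 3, about 27% without a pair because poor responders are lost), the paired bias was +0.88 to +0.98 and the likelihood-based bias +0.88 to +0.91. Neither method repairs this.

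**6. Use of injury status.** When the change itself is assumed to vary with severity (true mean +0.15), adding severity as a main effect left +0.161. Estimating severity-specific changes and averaging them over all patients gave +0.150, at about the same standard error. The gain comes from the interaction with visit and the averaging, not from the covariate alone.

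**The case against.** The strongest defence is that bias is possible but not demonstrated. The explicit VO2peak exclusions are written for sub study 2, which tests at discharge, and the same sub study offers very deconditioned patients an arm-crank ergometer. Applying them to admission in the primary study is inference. The untestable share may be small. In step 4 the paired biases (for example 0.166 − 0.15 = 0.016 and 0.022 − 0.05 = −0.028) are below one standard error. All of this stands, and it limits the claim to a risk. It does not remove the link between testing and injury in Ethical considerations, or the lack of any plan for the missing values.

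Four stronger readings are tempting and should be resisted:

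- A reader might multiply 70 by 18/12 to get 105 admissions, set this against 50–60, and infer that 43–52% fall outside the analysis. But the primary-study period includes follow-up, so 105 is not the pool that could complete, and the Statistics section expects 50–60 included.
- A reader might infer that the paired estimate is biased, and upwards. Steps 2 to 4 allow either sign, or none.
- A reader might infer that a mixed model rests on a weaker assumption. It does not: the paired test tolerates missingness tied to a patient's stable level, which the random-intercept model does not. The mixed model tolerates missingness explained by observed visits, which the paired test does not. Neither assumption contains the other.
- A reader might infer that the third visit and the neurological data are thrown away. The Statistics section reports all three visits descriptively, and the tertiary-outcome text makes neurological classification a first choice for analysis against the primary outcome. They are simply not used in the stated test of change.

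**Conclusion.** The point holds as a risk that the plan should address. The VO2peak change is estimated only in patients testable at both visits, testing depends on injury severity, and nothing in the plan checks or limits the consequence. The documents do not determine the direction or size; the 24% illustration and both simulations rest on assumed missing shares, spreads and mechanisms. If change is similar in patients with and without pairs, there is no bias.

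The case for changing the analysis does not rest on a mixed model being better in general. All three visits and the ISNCSCI grading are already planned, and severity is the one driver of testing that the plan names. An analysis that conditions on it, set beside the paired test, shows how far the answer depends on who was tested. Patients never tested on VO2peak remain outside both analyses except through assumption.

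**What to change.** In the Statistics section:

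1. Name the primary contrast for VO2peak and the population it should describe.
2. Analyse VO2peak and the other continuous outcomes at all the visits where they are measured, in a mixed model for repeated measures that includes every consenting patient with at least one measurement. Use visit, admission AIS grade and neurological level (grouped coarsely, given 50–60 patients, for example motor complete or not and tetraplegia or paraplegia), and the interaction of each with visit. Report the change averaged over the injury mix of all included patients.
3. Keep the paired t-test beside it, and state the missing-data assumption of each.
4. Add a missing-not-at-random sensitivity analysis, for instance by letting r in step 3 vary over a stated range.
5. Tabulate numbers tested and reasons for no test at each visit, and say plainly that patients never testable are not covered.
6. Reconcile the primary-study and Statistics sections on whether 50–60 means patients included or complete data sets.

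This applies to change within the intervention cohort; Sub study 1 lists VO2peak in the historic control at discharge only. No new data are needed beyond the reasons for missed tests. The costs are SAP wording, slightly more analysis, and reliance on data missing at random given observed visits and injury status. Little or no gain in precision should be expected. The outcome section indicates that some analyses have already been done, so if VO2peak is among them the model should be reported as added at this revision.

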The study consists of a primary study designed as a controlled pre-post multi modal pragmatic clinical intervention study, with 6-months of follow up and a historic control conducted as a prospective cohort study

Sub-investigations

BMI is considered a high risk determinant due to the impact of overweight on the cardiovascular risk profile and level of functioning [3]. Therefore a prospective representative longitudinal national survey of BMI is conducted in collaboration with Spinal Cord Injury Center of Western Denmark, before the onset of the controlled intervention, and serves as historic control (sub-study 1).

Additional objective outcomes measures will be collected at CSCI during the historic survey period including physical activity, physical capacity and body composition. Accordingly, two sub-studies regarding test – retest reliability of a VO₂ peak test (sub study 2) and a multi sensor accelerometer (sub study 3) respectively will be performed for two reasons. First, VO₂ peak and accelerometry are considered valid methods to measure the effect, amount and intensity of physical activity at discharge from the primary SCI rehabilitation. Secondly, these measures will be collected

repeatedly during the prospective controlled implementation study and serve as individual ¹ motivational components in the patient-clinician educative PA communication, besides being exact outcome measures. For this reason assessing the test retest reliability of the two procedures is essential (see timeline in figure 2).

Participants and eligibility criteria

All newly injured patients within the last 12 months with a SCI admitted at CSCI are included regardless of , etiology to the spinal cord lesion, neurological level or completeness* 1 of the lesion

if informed consent is retrieved and they are 18 years of age or older. In sub study 1 all newly injured people with SCI admitted at the SCI Centre of Western Denmark are also included.

Exclusion criteria for the VO2peak test in sub study 2 includes motor complete SCI (AIS A and B) at C4 level or above, and assisted ventilatory function. Other exclusion criteria are the presence of decubitus, severe spasticity or musculoskeletal problems considered at risk of aggravation during testing or preventing completion of the test.

Sub study 3 includes a convenience sample of 20 patients aiming at ensuring a broad variation of age, gender, neurological level and completeness of SCI.

Methods and analysis

Patient involvement

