and blood samples describing metabolic profile. BMI is part of usual care while body composition evaluated by a body scan (DEXA) is part of usual care at discharge, and therefore the study applies one additional scan to the patients. Measure of shared decision making related to the two patient decision aids for PA and healthy diet (Shared Decision Making Questionnaire (SDM-Q-9)) is only used at discharge. Amount of physical activity (Leisure Time

Physical Activity Questionnaire for people With Spinal Cord Injury (LTPAQ-SCI)), self- assessed ability to be physically active (Exercise Self Efficacy Scale for people with Spinal Cord Injury (ESES)),

The following assesments were not a part of standard rehabilitation: Physical capacity is assessed by exercises already being a part of standard rehabilitation and the assessment is non-invasive while a mask covering nose and mouth measures the patients expired air. The patients ventilation is not impaired and the patient can terminate the test at any time. Physical activity is measured by an activity monitor attached to the patient's chest by two surface electrodes and is non-invasive. The monitor is individually calibrated to the patients by heart rate measures obtained during the assessment of physical capacity. *This outcome was not implemented as intended, due to low feasibility of the procedures needed for individual calibration in the clinical setting.*

The patients will perform the daily activities they would do regardless of the assessment and no new task will be required. The assessments of physical capacity and physical activity will be assessed twice to measure the reproducebility of the measurements. A blood sample (5ml) will be collected at the same time as a standard blood sample related to standard rehabilitation is collected. In this way only one needlestick will be applied to the patient. The analysis describing metabolic profile will be performed immediately after and the blood sample will not be stored.

Outcome measures evaluating the intervention comprises furthermore more of the following tertiary outcomes:

Tertiary outcomes

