This study includes all patients with a new SCI hospitalized at CSCI or SCI Center of Western Denmark during a period of 10 months whereby 100 patients are expected to participate. Data concerning BMI, level of functioning (SCIM III) and neurological status (ISNCSCI) are collected at both centers. Patients with a new SCI (within the last 12 months) who are admitted for rehabilitation several months after the time of injury, are also included in the prospective survey. Therefore BMI at the time of injury is collected for all patients at admission to primary rehabilitation from both the patient's medical record and by asking the patient about weight and height at the time of injury. At CSCI, BMI every 6 week, quality of life (QoL SCI), depression (PHQ-2), amount of physical activity (Leisure Time Physical Activity Questionnaire for people With Spinal Cord Injury (LTPAQ-SCI)) and self- assessed ability to be physically active (ESES) will be collected additionally during this period, at admission, discharge and at follow up 6 months after discharge. A measure for physical capacity (VO2peak), physical activity(Actiheart multisensor accelorometer) and bodycomposition (DEXA) is performed as well at discharge. Data from this sub study serves as a historic control for the Intervention study.

Sub study 2. Test-retest reliability of a VO2 peak test

[figure not shown]
This study includes all patients participating in sub study 1 who are able of performing the test at discharge from primary rehabilitation. The patients are allocated by randomization to a test session of either intra- or interrater reliability. Four different pre -defined exercise protocols are used due to the complexity of a SCI in order to reach pre-defined criteria for VO2peak. For people with an incomplete SCI, a seated cross-trainer is used (NuStep T5XR®) with incorporated standard- and a modified test protocol in the equipment software. Equipment and modified protocol is reliable in people with traumatic brain injury and has been validated in healthy persons [33, 34]. In people with an incomplete SCI the equipment is safe, and involves a large amount of muscle mass ensuring completion of the test [35]. In case the equipment and protocols are difficult to use for

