people with a complete tetraplegia, paraplegia or very deconditioned patients, which may hinder reaching VO₂peak, an armcranking ergometer will be used (SCI FIT Pro1®). The test protocols used on the SCI FIT armergometer is established from the most common protocols for people with tetra and paraplegia during rehabilitation, reported in a recent systematic review [36]. If predefined criteria for VO₂peak is not reached at test 1, a more suitable protocol is chosen for test 2 in order to reach VO₂peak, and retested at test 3. The test-retest study takes place at discharge, separated by 48 hours or within maximum 5 days between tests at the same time of the day. The participants refrain from caffeine, alcohol and intensive physical exercise on the day of testing as well as tobacco smoking two hours before the test. Bladder emptying is to be performed before the test. The measurement is non-invasive while the patients expired air is analyzed through a mask covering the patients mouth and nose and with unimpeded respiration. The patient decides when the test is terminated.

Sub study 3. Test-retest reliability of a multi censor accelerometer.

This study includes a convenience sample of 20 patients ensuring a representative sample of para and tetraplegia, complete and incomplete injuries, age and sex. The equipment used for monitoring amount and intensity of PA consists of sensors registering acceleration and heart rate, and is placed on the thorax of the participant with two surface electrodes. The equipment has previously been used in wheelchair dependent people with SCI, although the reliability of the equipment in an inpatient setting has not previously been assessed [37]. The precision of the equipment is higher when calibrated individually to the participant using measures of energy expenditure during rest and during an exercise testing whereby heart rate is retrieved as well. [68]. In this study individual calibration will be made and during the VO₂peak test described in sub study 2, and continuous measurements of amount and intensity of PA will be made during a period of 2- 4 days, where the patients will be physically active just as normal. The patients will not be performing new tasks or physical activities. The test-retest is performed 4 -2 weeks before discharge on identical days of the week , over a period of two weeks.

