Figure 1. Timeline and outcome measures used in the historic control study (A) at the Spinal Cord Injury Center of Western Denmark (SCICWD) and the Department for Spinal Cord Injuries in Eastern Denmark (DSCIED). Timeline and outcome measures used in the intervention study at DSCIED (B) (Source: Protocol article)

VCR: Center for Spinal Cord Injury, Western Denmark; **CSCI:** Clinic for Spinal Cord Injuries, Eastern Denmark; **BMI:** Body Mass Index; **SCIM:** Spinal Cord Injury Independence Measure; **ISNCSCI:** International Standards for Neurological Classification of Spinal Cord Injury; **PHQ-2:** Patient Health Questionnaire- 2; **QOL SCI:** International SCI Quality of Life Basic Data Set; **LTPAQ-SCI:** Leisure Time Physical Activity Questionnaire for people with Spinal Cord Injury; **ESES:** Exercise Self Efficacy Scale ; **AH** Actiheart (accelerometer); **VO2peak:**peak oxygen uptake; **DXA:** Dual-energy X-ray Absorptiometry; **MP:** Metabolic profile; **NORMON:** Nordic monitoring of diet, physical activity and overweight; **SDM-Q-9:** 9-item Shared Decision Making Questionnaire

Outcome measures

All outcome measures will be collected at admission, discharge and follow-up 6 months after discharge. At CSCI data for BMI is also collected every 6`th week during the hospitalization period.

Primary outcome

- Oxygen uptake: Is measured as VO₂peak during a maximal exercise test and is gold standard for measuring aerobic capacity. For people with a SCI several test protocols have been used [36].

Secondary outcomes

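### Does the lack of a rule for keeping one ergometer across visits undermine the paired analysis of VO2peak?

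*Combined protocol and SAP*

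**What the plan says.** The Intervention section makes VO2peak the primary outcome. On timing, the Outcome measures section states: "All outcome measures will be collected at admission, discharge and follow-up 6 months after discharge". The Statistics section reports change over time by paired t-test, with no term for test equipment, and says no power calculation was done.

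For the intervention study itself the method is generic. The Intervention section says "Physical capacity is assessed by exercises already being a part of standard rehabilitation", and the Outcome measures section refers only to a maximal exercise test. Neither names a machine.

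Equipment appears under Sub study 2, the test-retest study carried out at discharge: "For people with an incomplete SCI, a seated cross-trainer is used". The same section says that this machine "involves a large amount of muscle mass ensuring completion of the test". The arm crank is a fallback. It is used when the cross-trainer is hard to use for people with complete tetraplegia or with paraplegia, or for "very deconditioned patients, which may hinder reaching VO₂peak, an armcranking ergometer will be used". Four protocols are defined, and the cross-trainer alone carries a standard and a modified one. If the criteria for a peak are not met at the first test, "a more suitable protocol is chosen for test 2 in order to reach VO₂peak, and retested at test 3", with tests no more than 5 days apart.

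The link to the intervention study is in Sub-investigations. Because VO2peak and accelerometry will be collected repeatedly there, "assessing the test retest reliability of the two procedures is essential".

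**The concern.** Conditioning helps decide the machine, and conditioning is what the primary outcome measures. A patient too deconditioned for the cross-trainer at admission may manage it at discharge. Completeness of injury is also re-examined during the study. The cross-trainer is described as using a large muscle mass, so the two machines need not read alike in the same person. If a patient moved from arm crank to cross-trainer, the paired difference would add a device effect to any gain in fitness, and the paired t-test would not tell them apart.

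The historic control may offer no check. Sub study 1 lists its VO2peak at discharge only, which gives no within-patient change to compare with. The general sentence on visits in Outcome measures reads more widely. That tension is a separate matter of wording.

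**Working it through.** There is no stated figure to reproduce: the plan gives no effect size, SD, switching rate or device offset for VO2peak. Every input below is assumed except n, for which Statistics and the Primary study section expect 50–60 patients, and the 24% rise in VO2peak during early rehabilitation cited in the background.

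**1. Shift in the mean change.** Let *s* be the net share switched from arm crank to cross-trainer and *δ* the offset as a percentage of baseline. Shift = *s* × *δ*.

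| s | δ | shift (points) | relative to 24 |
|---|---|---|---|
| 0 | any | 0 | 0 |
| 0.05 | 5 | 0.25 | 1% |
| 0.10 | 10 | 1 | 4.2% |
| 0.20 | 20 | 4 | 16.7% |
| 0.30 | 30 | 9 | 37.5% |

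The sign reverses for net switching the other way, and balanced switching gives zero.

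**2. Effect on the test.** Suppose the true change is zero, the SD of percentage change is σ, and a normal approximation to the paired test is used with total SD = √(σ² + δ²s(1−s)). At n = 50–60 the two-sided 5% test rejects in:
- 10% switched, offset 10: 7.5–8.0% (σ = 15) or 5.9–6.1% (σ = 25)
- 20% switched, offset 20: 38–45% (σ = 15) or 19–22% (σ = 25)
- 30% switched, offset 30: 88–93% (σ = 15) or 61–69% (σ = 25)

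The problem would therefore be real if switching were common, one-directional and accompanied by a large offset. It is slight if switching is occasional and the offset modest.

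**3. What a same-ergometer analysis would deliver.** Let *μ* be the mean change in patients who stay on one machine and *τ* the extra true gain in those who switch.
- All pairs: (1−s)μ + s(μ+τ+δ) = μ + s(τ+δ)
- Same-ergometer pairs: μ
- Gap: s(τ+δ)

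Only the sum τ+δ can be estimated. With s = 0.3, an offset of 10 and no extra gain gives a gap of 3 points; an extra gain of 10 and no offset also gives 3. Over s = 0.1 to 0.3, an extra gain of 10 alone gives 1 to 3 points with no device effect at all.

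The true mean change for everyone is μ + sτ. The all-pairs result misses it by +sδ and the same-ergometer result by −sτ. With s = 0.2, δ = 5 and τ = 10, the errors are +1 and −2 points, so dropping mixed pairs would do worse. An extra true gain is plausible, since patients would leave the arm crank because they had recovered.

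**4. Precision.** Half-width of the 95% CI = t(0.975, n−1) × SD/√n, for an SD of change of 20–30 points: 5.4–8.1 with 55 pairs, 6.1–9.1 with 44, and 6.6–9.9 with 38. For the gap, with *k* switched and *m* not switched, half-width = 1.96 × (k/n) × SD × √(1/k + 1/m). At n = 55:
- k = 5: 1.7–2.5 points
- k = 11: 2.6–4.0 points
- k = 17: 3.5–5.3 points

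A 1-point gap at about 10% switching would be lost in noise. A 4-point gap at 20% could be seen, but step 3 shows that its cause could not be named.

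**The case for a change.** The strongest case for acting is that the gap is certain and sits on the primary outcome, while a table of machine by visit costs little. If the Sub study 2 procedure is not the one used at the intervention visits, then no equipment procedure for the primary outcome appears in the text at all. The rule for changing protocol shows the team foresaw that a first choice might be unsuitable, and it covers only tests a few days apart at discharge.

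Part of this stands. No text found fixes the machine or protocol across the three visits, or says how a mixed pair is handled. Two figures could not be read here, so this applies to the text only.

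The step from that gap to a fault does not stand. Reuse of the procedure is inferred from the reason given for the reliability studies. Even the eligibility text is confined to "Exclusion criteria for the VO2peak test in sub study 2". Nothing shows that patients switched, and the arm crank depends on the cross-trainer being difficult, so a patient with complete injury may never leave the cross-trainer. The offset has no size. The retest at test 3 on the newly chosen protocol suggests the team already favours like-for-like pairs. A same-ergometer restriction would also miss a change between the two cross-trainer protocols.

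**Conclusion.** No change to the plan. This is a missing operational detail, and nothing in the documents shows that the paired t-test as written gives a wrong answer. The shift in mean change is unknown and may be zero; 0 to 9 percentage points is an illustration that rests wholly on assumed switching and offset of 0–30% each.

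A rule added now would bring little. The all-pairs change would remain the main result. A same-ergometer result beside it would be less precise, would select on events after baseline, and would settle nothing whether or not it agreed. The plan already describes itself as revised because some outcomes were not analysed as intended, so an added analysis might also have to be labelled post hoc.

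An analyst writing up VO2peak would ordinarily state which machine and protocol were used at each visit, where test records show it. If all pairs match, the question closes. If some do not, the most that can be said is that device effect and true extra gain in those patients cannot be separated. That is a matter for the report. The conclusion would change only if records showed frequent switching in one direction between machines known to read far apart.
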